8.3.3. Treatment Comparisons

Demographic and baseline characteristics (e.g., gender, age, racial or ethnic origin, height and weight, body mass index (BMI), blood pressure and other characteristics) will be summarized for each treatment group. In addition, smoking and alcohol habits, diabetic and cardiovascular medical history, baseline laboratory results, and prior medications will be summarized by treatment group. Binary and ordinal characteristics will be summarized by counts and percentages, while continuous variables will be represented by mean and standard deviations or medians and percentiles, as appropriate. Any variables with treatment imbalances may be considered as covariates for further analysis of an exploratory nature. Such covariates will be identified on the basis of the clinical relevance of the observed treatment difference.

8.3.3.1. Primary Comparisons of Interest

The primary endpoint will be the time to the first occurrence of MACE over the full duration of the study. A p-value for non-inferiority of the primary endpoint will be calculated from a Cox Proportional Hazards (PH) regression model with treatment group as the only covariate for the hypotheses described in Section 8.1. If non-inferiority is established, a p-value for superiority for the primary endpoint will be calculated from a Cox Proportional Hazards (PH) regression model with treatment group as the only covariate for the hypotheses described in Section 8.1.

8.3.3.2. Other Comparisons of Interest

For other analyses incidence rates will be presented for binary data and summary statistics (mean, median, standard deviation, minimum, and maximum) will be presented for continuous data. Time to event endpoints will be evaluated via the p-value from a Cox PH regression model with treatment as the only covariate. Furthermore, summary statistics of change from baseline for HbA1c will be presented along with percent of subjects within ranges of clinical interest (e.g., HbA1c < 7.0%). Available lipid data will be summarized for descriptive purposes.

8.3.4. Interim Analysis

An IDMC will monitor progress of the study and ensure that it meets the highest standards of ethics and subject safety. All cardiovascular event data, together with other safety data, will be sent to the IDMC for review at approximately every 6 months after the first subject has been randomised to receive treatment. This frequency may be adjusted, if deemed necessary by the IDMC, depending on the enrolment rates and the rate of safety events. There are no plans to stop the study early for a non-inferiority or benefit claim, however should the IDMC identify in the course of its scheduled reviews overwhelming evidence of MACE benefit (e.g., $p < 0.001$), with directionally consistent findings on all-cause mortality, the IDMC might consider recommending early stopping. This approach essentially preserves the final alpha for the end-of-study analysis at 5% and hence there are no plans to adjust the final alpha on account on safety reviews conducted by the IDMC. The IDMC charter, reporting and procedures are outlined in separate documents.

8.3.5. Multiplicity Controls

If non-inferiority is established for the primary endpoint, the data will be used to test for evidence of superiority. This approach is a closed testing procedure, and therefore, no adjustment for multiplicity is required [Hung, 2009].

Other Secondary Endpoints and Subgroup Analysis

The following secondary endpoints will provide supportive evidence for cardiovascular safety and metabolic efficacy and will not use any multiplicity adjustment procedure. Results will be presented with confidence interval and nominal p-values:

Components of primary endpoint (MACE = cardiovascular death, MI, stroke)

MACE + urgent revascularisation for unstable angina

Cardiovascular death or hospitalisation for heart failure

Time to initiation of insulin of more than 3 months duration for those subjects not treated with insulin at study start

Time to initiation of prandial insulin in those subjects treated with basal insulin at study start.

The proportion of subjects achieving glycaemic control ($\text{HbA1c} \leq 7.0\%$ at final assessment) with no severe hypoglycaemic incidents and weight gain $<5\%$ of body weight

Mean HbA1c at scheduled visits and change from baseline

Mean body weight at scheduled visits and change from baseline

Mean eGFR at scheduled visits and change from baseline

Composite microvascular endpoint

To examine the degree of consistency of the overall treatment effect in terms of important prognostic factors, subgroup analyses of the primary outcomes will be performed based on subject demographics and baseline characteristics. These exploratory subgroup analyses will not be adjusted for multiple comparisons and will be interpreted descriptively.

8.3.6. Key Elements of Analysis Plan

Any deviations from the original analysis planned in the protocol agreed upon prior to finalization of the RAP, will be described in that document. Any additional changes to the planned analysis in the RAP will be described in the final clinical study report.

8.3.6.1. Primary Analysis

The primary analysis is an ITT analysis of the time to the first occurrence of MACE over the full duration of the study. Time to event analyses will be performed using Cox's Proportional Hazard regression with SAS PHREG with treatment group as the only covariate. Data for subjects without a primary event will be censored.

Treatment differences will be estimated via the hazard ratio and its 95% confidence interval (CI).

The hypothesis of non-inferiority of albiglutide relative to placebo group with hazard ratio less than 1.3 with respect to cardiovascular risk will be tested at the end of the study. If non-inferiority is established, the hypothesis of superiority of albiglutide relative to placebo will be tested.

The absolute risk difference per 100 PY, with its associated 95% confidence interval, will also be presented.

The product-limit estimates of the probabilities (and their standard errors) of first MACE over time will be computed and displayed as Kaplan-Meier (KM) survival curves for albiglutide and placebo groups. The KM curves will also be presented corresponding to the above comparisons.

The total number of all MACE or any of its components will be analyzed by Poisson regression model. The incidence rate per 100 person-years, relative risk and their 95% CI will be presented. Number of subjects who experienced at least one event, 2 or 3 or more MACE or its components will also be summarized by treatment group.

As sensitivity analyses, the analyses described above will be repeated using events occur while on-treatment and events occur during the period of on-treatment plus 56 days post last dose.

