2. OBJECTIVES AND ENDPOINTS

| Objectives | Endpoints |
|--|--|
| Primary | |
| To assess the effect of albiglutide with respect to MACE when added to glycaemic standard of care versus standard of care alone | 
Time to first occurrence of MACE (cardiovascular death, myocardial infarction, or stroke)
 
The primary analysis will be non-inferiority. If the pre-specified non-inferiority criterion is met then superiority testing will be performed¹
 |
| Secondary | |
| To supplement the primary objective by further characterization of the effects of albiglutide on cardiovascular outcomes | 
 • Time to first occurrence of the following: 
 ▪ MACE or urgent revascularisation for unstable angina ▪ The individual components of the primary endpoint ▪ Cardiovascular death or hospitalization due to heart failure |
| To evaluate the effects of albiglutide on metabolic management of type 2 diabetes | 
 • Time to initiation of insulin of more than 3 months duration for those subjects not treated with insulin at study start • Time to initiation of prandial insulin in those subjects on basal insulin at study start • The proportion of subjects achieving glycaemic control (HbA1c \leq 7.0% at final assessment) with no severe hypoglycaemic incidents and weight gain $<$5% of body weight • The time to first occurrence of a clinically important microvascular event (see Section 6.2.4) • Change in HbA1c • Change in body weight • Patient reported outcomes from TRIM-D/EQ5D |
| To evaluate the safety of albiglutide | 
 • All cause mortality • Non-fatal SAEs • AEs leading to discontinuation of investigational product • AE of special interest (see Section 6.2.3) • Change in eGFR calculated using MDRD formula • Change in blood pressure and heart rate |
| Exploratory | |
| To evaluate patient reported experience of diabetes treatment | 
 • Patient reported outcomes from study specific questionnaire |

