6.2.2. Adverse Events (AE) and Serious Adverse Events (SAEs)

The definitions of an AE or SAE can be found in [Appendix 5](#).

The investigator or site staff will be responsible for detecting, documenting and reporting events that meet the definition of an AE or SAE.

For this study events of myocardial infarction, stroke, unstable angina requiring urgent revascularization, hospitalization for heart failure, TIA and sudden cardiac death will not be collected or reported as AEs or SAEs. These events will be collected separately,

subjected to blinded adjudication by an independent CEC using prespecified diagnostic criteria, and reported separately (Section 6.2.1.1). All other events that meet serious criteria as defined in [Appendix 5](#) should be reported as SAEs.

All events with an outcome of death will be adjudicated to classify the cause of death as specifically cardiovascular or non-cardiovascular. Any event resulting in death should be reported as a SAE unless the event is myocardial infarction, stroke, unstable angina w/ urgent revascularization, Heart failure, TIA or sudden cardiac death which the protocol specifies are not to be collected as adverse events.

The study will not collect all non-serious AEs. Non-serious AEs leading to discontinuation of investigational product and non-serious AEs of special interest (see Section 6.2.3) will be collected.

Any events not specifically addressed above should be reported as an AE or SAE according to the definitions in [Appendix 5](#).

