8.3.6.2. Secondary Endpoint Analysis

Endpoints that supplement the primary objective by further characterization of the effects of albiglutide on cardiovascular outcomes endpoints:

Supportive endpoints including the time to first occurrence of adjudicated MACE or urgent revascularisation for unstable angina, time to first occurrence of individual components of MACE, time to first occurrence of cardiovascular death or hospitalisation for heart failure will be analyzed using a proportional Cox regression model similarly as the primary endpoint.

Endpoints that evaluate the effects of albiglutide on metabolic management of type 2 diabetes:

Among the subjects who are not on insulin at baseline (NI population), time to insulin will be analyzed using a proportional Cox regression model similar to the primary MACE analysis. The product-limit estimates of the probabilities (and their standard errors) of adding insulin over time will be computed and displayed as Kaplan-Meier (KM) survival curves for albiglutide and placebo treatment groups. The KM curves will also be presented corresponding to the above comparisons.

The composite of the proportion of those achieving good control ($HbA1c \leq 7.0\%$) AND having no severe hypoglycaemic incidents AND weight gain $<5\%$ at the end of the study will be evaluated utilize nonparametric, covariance-adjusted, extended Mantel-Haenszel tests. Additional analysis will be provided for scheduled visits. Nominal p-values and 95% CIs will be presented for these visits. Time to introduction of prandial insulin in those on basal insulin \pm orals anti-hyperglycemic drugs at baseline will be analyzed using a Cox PH model and KM method similar to the primary endpoint.

Composite of microvascular events will be analyzed using a proportional Cox regression model and KM method similar to the primary endpoint.

HbA1c, body weight and eGFR will be analyzed using a repeated mixed effect model. The least square means, 95% CIs and nominal p-values will be presented.

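### Kaplan-Meier probabilities of insulin start, prandial insulin and microvascular events censor deaths and so slightly overstate cumulative risk

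*Protocol*

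**What the plan says.** All references are to the protocol as amended by Amendment 3.

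- **First MACE.** Section 8.3.6.1: "The product-limit estimates of the probabilities (and their standard errors) of first MACE over time will be computed" and shown as Kaplan-Meier curves by arm. The same section states: "Data for subjects without a primary event will be censored". Section 2 defines the endpoint as "Time to first occurrence of MACE (cardiovascular death, myocardial infarction, or stroke)", so cardiovascular death is an event and any other death is not.
- **Insulin start** (subjects not on insulin at baseline). Section 8.3.6.2 uses parallel wording: "The product-limit estimates of the probabilities (and their standard errors) of adding insulin over time".
- **Prandial insulin** (subjects on basal insulin). Section 8.3.6.2: "analyzed using a Cox PH model and KM method similar to the primary endpoint".
- **Microvascular events.** Section 8.3.6.2: "Composite of microvascular events will be analyzed using a proportional Cox regression model and KM method", again following the primary endpoint. Section 6.2.4 defines these as dialysis or transplant, blindness and eye procedures; death is not a component.
- **MACE components.** Section 8.3.6.2 lists "time to first occurrence of individual components of MACE" among the endpoints for a Cox model. It names no Kaplan-Meier estimate for them.

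Section 8.3.2 sets censoring dates for loss to follow-up, for the on-treatment and on-therapy analyses and for all-cause mortality. It has no rule for a death that is not part of the endpoint. Section 6.2.2 provides that "All events with an outcome of death will be adjudicated to classify the cause of death as" cardiovascular or not, so the competing event will be in the database.

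**The concern.** A subject who dies can no longer start insulin, add prandial insulin or have an eye procedure. Censoring that subject at death makes Kaplan-Meier behave as though the subject could still have the event later at the same rate as the survivors. One minus Kaplan-Meier then describes a setting in which nobody dies first. It is larger than the share of randomised subjects who will have had the event.

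The protocol names the estimator and says that it estimates probabilities, so this is a stated choice and not simply a detail left open. At stake is the accuracy of displayed absolute risks, mainly for insulin start. Section 3.4.2 presents delay of insulin as a possible benefit that the trial will assess.

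**Working it through.** **The plan's own figures.** The protocol states no cumulative risk that can be checked directly. Its sample-size figures do reproduce:

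- Events: 4 × (1.960 + 1.282)² / (ln 1.3)² = 4 × 10.507 / 0.06883 ≈ 611, as in Section 8.2.1.
- Mean follow-up: 611 / (9400 × 0.02) = 3.25 years and 611 / (9400 × 0.03) = 2.17 years, against the stated 3.2 and 2.2.

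**Formulas.** With constant hazards, λ for the event and c for competing death:

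- One minus Kaplan-Meier, deaths censored: 1 − exp(−λt)
- Cumulative incidence: λ/(λ + c) × [1 − exp(−(λ + c)t)]

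The first exceeds the second whenever c > 0.

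**Inputs.** MACE rates of 2.0% and 3.0% a year with mean follow-up of 3.2 and 2.2 years come from Section 8.2.1. The median follow-up floor of 1.5 years is from the same section, and 4.9 years is the longest total duration in Table 3. The death, insulin-start and microvascular rates are assumptions, because the protocol gives none.

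**Insulin start at 3.2 years, any death competing.**

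- λ = 5%, c = 1%: 1 − exp(−0.16) = 14.79%; (0.05/0.06) × [1 − exp(−0.192)] = 14.56%; gap 0.23 points.
- λ = 10%, c = 3%: 1 − exp(−0.32) = 27.39%; (0.10/0.13) × [1 − exp(−0.416)] = 26.18%; gap 1.21 points.

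Gap in percentage points at other horizons:

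| Insulin start / death, per year | 1.5 y | 2.2 y | 3.2 y | 4.9 y |
|---|---|---|---|---|
| 5% / 1% | 0.05 | 0.11 | 0.23 | 0.50 |
| 5% / 3% | 0.16 | 0.33 | 0.67 | 1.46 |
| 10% / 1% | 0.10 | 0.21 | 0.41 | 0.86 |
| 10% / 3% | 0.30 | 0.61 | 1.21 | 2.50 |

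**Prandial insulin**, one illustration (12% a year, death 3% a year, 3 years): 1 − exp(−0.36) = 30.2%, against (0.12/0.15) × [1 − exp(−0.45)] = 29.0%.

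**Microvascular events**, at an assumed 1% a year and 3.2 years: 3.15%, against 3.10% to 3.00% for death at 1-3% a year. The gap is 0.05 to 0.15 points.

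**First MACE**, non-cardiovascular death assumed at 0.5-1.5% a year.

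- 2.0% a year at 3.2 years: 6.20% against 6.15% to 6.05%; gap 0.05 to 0.15 points.
- 3.0% a year at 2.2 years: 6.39% against 6.35% to 6.28%; gap 0.03 to 0.10 points.

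For scale, with 9400/2 = 4700 per arm, the binomial standard error at 6.4% is √(0.064 × 0.936 / 4700) ≈ 0.36 points. The MACE gap at 3.0% a year is less than a third of that.

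**The case against.** The strongest reply is that these curves are descriptive and nothing confirmatory depends on them. Non-inferiority and superiority rest on the Cox hazard ratio, and the absolute contrast in Section 8.3.6.1 is a rate difference per 100 person-years. Neither uses Kaplan-Meier complements. Censoring competing deaths is also the display that matches the cause-specific Cox model. A cumulative incidence curve depends on mortality as well: if albiglutide raised non-cardiovascular death, its MACE curve would fall and could hide harm. All of this stands. It is why the MACE curve should stay as Kaplan-Meier.

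It can also be said that the RAP, which is not at hand, may add competing-risk displays. That is possible, but the protocol already names the estimator and what it is meant to estimate.

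Three stronger readings are tempting, and the document does not support them:

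- A reader might infer that risks of MI, stroke and the other MACE components are overstated too. Section 8.3.6.2 specifies only Cox models for components, and it names Kaplan-Meier where it intends it.
- A reader might infer a material overstatement of MACE risk, for instance by taking 3% a year out to 4 years. Table 3 gives total durations of 3.0 to 3.8 years at that rate, so 4 years lies outside every scenario shown.
- A reader might infer a distorted treatment comparison. No between-arm difference in Kaplan-Meier probabilities is planned.

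**Conclusion.** The point holds as a minor one about presentation. For insulin start, prandial insulin and microvascular events, the planned estimator overstates the cumulative probability because every death competes. For insulin start the excess is about 0.2 to 1.2 percentage points at 3.2 years. This assumes constant hazards, death at 1-3% a year and start rates of 5-10% a year. It would be smaller at shorter follow-up and larger in the tail of the curves. The protocol does not give the size of the non-insulin population, so this excess cannot be set against sampling error.

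That deaths are censored is explicit for MACE. For the three metabolic endpoints it follows from the instruction to proceed as for the primary endpoint and from the absence of any other rule.

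For MACE the excess is negligible.

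**What to change.** In Section 8.3.6.2, report cumulative probabilities of insulin start, prandial insulin and microvascular events by the Aalen-Johansen cumulative incidence function, with death from any cause as the competing event. In Section 8.3.6.1, keep the Kaplan-Meier curve for first MACE and state on it that non-cardiovascular deaths are censored; a supplementary cumulative incidence curve is optional. Leave all Cox models, tests and the event target as they are.

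The cost is a little extra output. Deaths are already collected and classified, so no new data are needed. Because cumulative incidence also reflects mortality, each curve should be read beside the Cox hazard ratio and the all-cause mortality result. It is unbiased only if the remaining censoring, from loss to follow-up and study end, is non-informative.

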8.3.6.2. Secondary Endpoint Analysis

Endpoints that supplement the primary objective by further characterization of the effects of albiglutide on cardiovascular outcomes endpoints:

Supportive endpoints including the time to first occurrence of adjudicated MACE or urgent revascularisation for unstable angina, time to first occurrence of individual components of MACE, time to first occurrence of cardiovascular death or hospitalisation for heart failure will be analyzed using a proportional Cox regression model similarly as the primary endpoint.

Endpoints that evaluate the effects of albiglutide on metabolic management of type 2 diabetes:

Among the subjects who are not on insulin at baseline (NI population), time to insulin will be analyzed using a proportional Cox regression model similar to the primary MACE analysis. The product-limit estimates of the probabilities (and their standard errors) of adding insulin over time will be computed and displayed as Kaplan-Meier (KM) survival curves for albiglutide and placebo treatment groups. The KM curves will also be presented corresponding to the above comparisons.

The composite of the proportion of those achieving good control ($HbA1c \leq 7.0\%$) AND having no severe hypoglycaemic incidents AND weight gain $<5\%$ at the end of the study will be evaluated utilize nonparametric, covariance-adjusted, extended Mantel-Haenszel tests. Additional analysis will be provided for scheduled visits. Nominal p-values and 95% CIs will be presented for these visits. Time to introduction of prandial insulin in those on basal insulin \pm orals anti-hyperglycemic drugs at baseline will be analyzed using a Cox PH model and KM method similar to the primary endpoint.

Composite of microvascular events will be analyzed using a proportional Cox regression model and KM method similar to the primary endpoint.

HbA1c, body weight and eGFR will be analyzed using a repeated mixed effect model. The least square means, 95% CIs and nominal p-values will be presented.

Additional analysis will be performed to assess the incidence rate of recurrent severe hypoglycaemic events between treatment groups during the course of the study. A repeated Poisson regression model including treatment and visit as factors will be used to test treatment difference with offset for person years. An unstructured working correlation matrix will be used in the iterative estimation process. The model-adjusted least square incidence rate for each treatment as well as the treatment difference of the incidence rate will be reported. Events of severe hypoglycaemia will also be summarized descriptively by treatment group. Additional summary by baseline HbA1c, renal status and age subgroup will also be provided.

Further analysis details will be provided in the RAP.

8.3.6.3. Subgroup Analysis

Separate subgroup analyses of the primary outcomes will be performed based on subject demographics and baseline characteristics. Subgroups may include sex, age group, BMI, whether subjects have history of a previous cardiovascular event, and baseline HbA1C, background of anti-hyperglycaemia treatment etc. The detail of subgroups will be pre-specified in the RAP. Consistency of treatment effects will be assessed using Cox regression, along with the 95% confidence intervals for the relative risk or hazard ratios for each subgroup a nominal alpha level for interaction of 0.10 will be used. The effect of treatment interaction with subgroups will also explored; however as the number of these subgroup variables may be large, the probability of observing at least one statistically significant result may be high. Thus these additional analyses will be considered exploratory regardless of the p-value associated with any interaction.

Further details will be provided in the RAP.

